3.2.1.4 Research Inclusion Criteria

1. The clinician in the CYPGS believes that GnRHa for a period of 2 or more years may be helpful to the CYP. Particularly, there is no current plan to initiate cross-sex hormone treatment during the trial period.
2. Written informed assent and consent from CYP and parent/legal guardian respectively.
3. The CYP and their parent have reviewed the suite of measures, including physical health investigations, cognitive assessments and questionnaires, and understand that their completion is required for the clinical trial.
4. Participants who are sexually active agree to use contraception throughout the trial.

3.2.1.5 Research Exclusion Criteria

1. The CYP has previously taken or is currently using GnRHa for this indication. This will be identified by (i) asking CYP and their parents/legal guardians about off-label use and (ii) through hormone blood tests at baseline (all participants) and for those randomised to delayed start at 12 months. Participants and their parents/legal guardians will be reminded about the safety and legal concerns of off-label use.
2. The CYP is or has taken cross-sex hormones for gender incongruence/dysphoria.
3. The participant is involved in another research trial*

* Specifically, a CTIMP or another intervention that could possibly interfere with involvement in PATHWAYS TRIAL or interpretation of the findings

Note. Sex steroids used in oral contraceptives either for birth control or management of dysmenorrhea is not an exclusion.

The electronic version of this document is the latest version. It is responsibility of the individual to ensure that any paper material is the current version. Printed material is uncontrolled documentation.

3.3 Eligibility Criteria for HORIZON INTENSIVE

CYP who are participants in PATHWAYS HORIZON will be eligible to take part in HORIZON INTENSIVE if they are not considered clinically eligible for GnRHa presently or in the future. Ineligibility may occur based on the preferences of the CYP and their parents/legal guardians or due to clinician view that they are not suitable for GnRHa either presently or in the future, and this view has been communicated to the CYP and their parents/legal guardians.

HORIZON INTENSIVE aims to include CYP with similar characteristics to TRIAL participants in relation to Gender Service of origin, birth-registered sex, Tanner stage and presence of neurodevelopmental disorders/high levels of traits. For initial identification, chronological age will be used as a proxy for Tanner stage, with self-reported Tanner stage acquired at baseline for matching purposes. Consideration will also be given to the amount of care they have received in the CYPGS so that this is roughly similar. To balance recruitment, the research team will identify from the research database potential participants to be approached for inclusion in HORIZON INTENSIVE. This selection will be informed by the above characteristics of TRIAL participants already recruited.

3.3.1 HORIZON INTENSIVE Inclusion Criteria

1. Participating in the PATHWAYS HORIZON study
2. Has agreed to be contacted for other research studies when assenting to PATHWAYS HORIZON

3.3.2 HORIZON INTENSIVE Exclusion Criteria

1. Is considered clinically eligible for GnRHa and wishes to receive this intervention
2. A decision regarding clinical eligibility for GnRHa is pending
3. CYP has previously used GnRHa or gender-affirming hormones for gender incongruence

3.4 Eligibility Criteria for PATHWAYS CONNECT

As per Table 1 above, participants in TRIAL and HORIZON INTENSIVE will be recruited to CONNECT. For TRIAL participants, they will be told about CONNECT when they are approached for TRIAL and will need to join CONNECT prior to randomisation in order to have a baseline MRI scan. For HORIZON INTENSIVE participants, they will be told about CONNECT at the same time as being approached for joining HORIZON INTENSIVE from HORIZON.

3.4.1 PATHWAYS CONNECT Inclusion Criteria

1. Participant is a member of PATHWAYS TRIAL or PATHWAYS HORIZON INTENSIVE.
2. Participant is willing to participate in brain imaging study, including travelling to London (King's College London).

The electronic version of this document is the latest version. It is responsibility of the individual to ensure that any paper material is the current version. Printed material is uncontrolled documentation.

3. Participant provides informed assent (for u16) or consent (for 16+).
4. Parent/legal guardian provides consent.

3.4.2 PATHWAYS CONNECT Exclusion Criteria

1. MR imaging is contra-indicated (e.g. ferro-magnetic metal implants).

3.5 Informed Consent

3.5.1 Informed Consent for TRIAL

3.5.1.1 The process of determining clinical eligibility

The process of determining clinical eligibility is set out in the clinical service document titled “PATHWAYS TRIAL for Gonadotropin Releasing Hormone Analogues (GnRHa) – Guidance for CYPGS clinicians” A schematic of the interplay between providing research information, determining clinical eligibility and then research eligibility is shown in Figure 3. This will involve a series of clinical meetings with the CYP both on their own and with their parents/caregivers/legal guardians focussing on known and unknown possible benefits and risks of GnRHa including possible longer-term risks, alternative interventions that may alleviate their symptom/distress. Information will be provided in written formats, supplemented with visual material and audio-recordings (e.g., of clinical discussions) adapted to meet the cognitive style of the CYP and their parents/caregivers/legal guardians. NHS interpreter services will be used for those who are not confident in their use of English. CYP and their parent/caregivers/legal guardians will be asked to demonstrate their understanding of GnRHa and alternative treatment approaches by answering questions from clinicians using their own words or alternative preferred communication (e.g., typing, audio recording). As part of the submission documents to the national MDT, CYP and at least one parent/legal guardian will be asked to provide their reasons for requesting GnRHa.

Specific attempts will be made to meet with both parents/legal guardians to elicit their independent views. Where there is a disagreement between parents/legal guardians about GnRHa, this will be flagged to the national MDT to consider in their decision.

While caregivers with parental responsibility will be encouraged to attend sessions to give their perspective and to support the CYP, it will be ultimately the views of parents and legal guardians whose views are formally considered in the clinical eligibility decision.

Fertility: The risks to long-term fertility will be discussed with each CYP considering GnRHa by a clinician in or attached to their Gender Service who has specific training and knowledge about fertility risks and options available to them as well as training in working with CYP experiencing gender incongruence. The information will include options around sperm donation and egg retrieval. CYP will be encouraged to ask questions and explore fertility preservation options prior to commencing on GnRHa

The electronic version of this document is the latest version. It is responsibility of the individual to ensure that any paper material is the current version. Printed material is uncontrolled documentation.

(if found clinically and research eligible). For those wishing to pursue fertility options at this time, a referral to specialist fertility preservation services will be facilitated by the Gender Service, noting that referrals are made either directly by paediatric endocrinologists or by the CYP's GP. There will be no upper limit imposed by research consent on how long young people have to consider and then explore fertility preservation options, and potential participants will be reminded of other constraints, e.g., around the upper age limit of the study.

Where there is clinical uncertainty about a CYP's suitability for GnRHa based on their physical health, e.g., low bone density, the relevant physical investigations will be undertaken prior to presentation at the NMDT, considered as screening investigations.

[figure not shown]

Figure 3. Pathway to TRIAL Eligibility

The electronic version of this document is the latest version. It is responsibility of the individual to ensure that any paper material is the current version. Printed material is uncontrolled documentation.

3.5.1.2 The process of informed consent to participate in TRIAL

CYP deemed clinically eligible for GnRHa and providing verbal consent to be contacted, will be contacted by the research team. The research team will confirm that the national MDT checklist was fully completed prior to the national MDT decision.

CYP and their parents/legal guardians will initially receive the standard paper PIS in clinic, but this may be supplemented by information in bespoke formats, to support the individual cognitive and learning styles of CYP and parents/legal guardians. CYP will be encouraged to read this information together with their parents/caregivers/legal guardians, prior to discussing it with a clinician in clinic. Specifically, researchers will check whether any bespoke sources of information were used to support the CYP's discussions with their clinical team in preparation for the clinical eligibility review by the national MDT. These information supports can be re-used and extended as needed by the CYP and their parents/legal guardians.

Following receipt of the information sheets, CYP and their parents/ legal guardians will discuss their participation with the Principal Investigator (PI) or delegated sub-investigator (SI) with GCP training. The PI/SI will further explain the purpose of the trial, the research procedures, and the potential benefits and harms associated with GnRHa, including possible long-term risks, and will establish the CYP and their parent/ legal guardian's comprehension of the information. The uncertainty about impact on long-term health and the importance of signing up to the NHS Registry to provide health information into adult life will be explained. This will usually involve seeing the CYP on their own in part, i.e., without a parent/legal guardian present. The CYP may have their clinical keyworker from the CYPGS present for additional support if they wish. Both parents/legal guardians are encouraged to be involved in the consenting process, where appropriate, and with at least one parent/legal guardian accompanying the CYP to ensure a supportive environment. While caregivers without parental responsibility may attend the meetings with the medical investigator, it will be made clear that it is only parents/legal guardians with parental responsibility who are involved in the decision, alongside the CYP. When caregivers attend the consenting process, parents/legal guardians will also be seen on their own. Where only one parent/legal guardian attends, the reasons for this will be recorded.

The PI/SI will check again that the possibility of fertility preservation was discussed with each CYP and their wishes to access this prior to GnRHa treatment will be recorded. Fertility preservation options should be discussed at each appointment considering endocrine and other medical options.

Informed consent will be obtained in person on paper from parents/legal guardians and assent from CYP by a PI/SI, following Good Clinical Practice (GCP) guidelines. The CYP and their parents/legal guardians will be specifically encouraged to take as much time as they need to make a decision.

The electronic version of this document is the latest version. It is responsibility of the individual to ensure that any paper material is the current version. Printed material is uncontrolled documentation.

For children, informed assent will include demonstrating understanding, retention, and the ability to weigh up the potential benefits and risks of participation, and to communicate their decision freely and without coercion. Clinicians must document the young person's and parent(s)' understanding of the trial, including direct quotes where possible, and ensure that both individual and joint discussions have taken place.

A standardised checklist—modelled on that used in the national MDT process—will be employed to ensure that all key aspects of the trial, including the nature of the intervention, potential risks (including those not yet known), implications for fertility, and the right to withdraw, have been thoroughly discussed and understood. Any safeguarding concerns, communication barriers, or co-occurring difficulties that may affect the young person's ability to assent or comply with trial procedures will be addressed and documented. Reasonable adjustments should be made where necessary. However, consent from a parent or legal guardian is required for the young person to participate in the research.

3.5.2 Informed Consent for HORIZON INTENSIVE

Participants will be recruited in person using paper consent forms. Recruitment may occur at any point during a participant's involvement in the broader PATHWAYS HORIZON study. However, researchers will aim to align recruitment into HORIZON INTENSIVE with the timing of annual assessments to optimise data collection intervals and minimise participant burden. To further reduce burden, the visit during which consent is obtained should ideally coincide with the collection of cognitive and physical health measures. This approach ensures that participants are not required to attend additional visits solely for consent procedures, and that data collection is streamlined.

3.5.3 Informed Consent for CONNECT

Informed assent/consent for CONNECT MR imaging will take place at the same time as enrolling in TRIAL or HORIZON INTENSIVE. It will follow the same route as that used for informed assent/consent for the main study, with separate participant information sheets (PIS) and informed assent/consent form.

4 Data Collection & Data Entry

4.1 Participant Timeline

Timepoint/Event	Screening (≤ 12 weeks to Day 0)	Baseline (Day 0)	Month 3 [+/- 2 weeks]	Month 6 [+/- 2 weeks]	Month 9 [+/- 2 weeks]	Month 12 [+/- 4 weeks]	Month 15 [+/- 2 weeks]	Month 18 [+/- 6 weeks]	Month 21 [+/- 2 weeks]	Primary outcome Month 24 [+/- 8 weeks]	Ongoing*
Registration form & consent	X										
Eligibility		X									
Medical history	X										
Demographic data	X										
Randomisation		X									
BASELINE CHARACTERISTICS #											
ADHD (SNAP-IV)		X									
Autism (SCQ)		X									
About Yourself Questionnaire		X									
Status form			X	X	X	X	X	X	X	X	
QUESTIONNAIRES ##											
Quality of Life (KIDSCREEN-10)		X		X		X		X		X	X###
KIDSCREEN-52 – all domains		X		X		X		X		X	X###
Personal priorities		X				X				X	X###
Gender Identity Questionnaire^^^		X				X				X	X###
Social Transition Questionnaire		X				X				X	X###

The electronic version of this document is the latest version. It is responsibility of the individual to ensure that any paper material is the current version. Printed material is uncontrolled documentation.

Timepoint/Event	Screening (≤ 12 weeks to Day 0)	Baseline (Day 0)	Month 3 [+/- 2 weeks]	Month 6 [+/- 2 weeks]	Month 9 [+/- 2 weeks]	Month 12 [+/- 4 weeks]	Month 15 [+/- 2 weeks]	Month 18 [+/- 6 weeks]	Month 21 [+/- 2 weeks]	Primary outcome Month 24	[+/- 8 weeks]	Ongoing*
Anxiety and depression symptoms (RCADS-25)		X	X	X		X	X	X		X		X ***
Suicide/ Self Harm (ASQ)		X	X	X		X	X	X		X		X ***
Gender dysphoria (UGDS-GS)		X				X				X		X ***
Body image/ dysphoria (BIS-GS)		X				X				X		X ***
Emotional Dysregulation (DERS-18)		X				X				X		X ***
Sexual Attraction Questionnaire		X				X				X		X ***
Romantic Relations (ALSPAC measure)		X				X				X		X ***
Parental support (PAGES)		X				X				X		X ***
Trauma (APCTSS)		X				X				X		X ***
Emotional & Behavioural Problems (CBCL, YSR)		X				X				X		X ***
Eating Problems (SCOFF)		X				X				X		X ***
SCANS												
DEXA+	X	X				X				X		X ***
Bone Age (X-Ray)	X	X				X^				X^		
CLINICAL MEASURES												
Tanner Staging**	X	X				X				X		
Self-reported Tanner Staging		X				X				X		
Physical examination	X	X		X		X		X		X		
***Vital signs	X	X		X		X		X		X		
ECG	X											

The electronic version of this document is the latest version. It is responsibility of the individual to ensure that any paper material is the current version. Printed material is uncontrolled documentation.

Timepoint/Event	Screening (≤ 12 weeks to Day 0)	Baseline (Day 0)	Month 3 [+/- 2 weeks]	Month 6 [+/- 2 weeks]	Month 9 [+/- 2 weeks]	Month 12 [+/- 4 weeks]	Month 15	Month 18 [+/- 2 weeks]	Month 21 [+/- 6 weeks]	[+/- 2 weeks]	Primary outcome Month 24	[+/- 8 weeks]	Ongoing*
Review of systems (history and examination)		X		X		X		X			X		
(Optional) Body Composition - Tanita Scale		X		X		X		X			X		
Telephone check-in			X		X		X		X		X		
Safety bloods	X	X		X		X		X			X		
***Pregnancy test (pocbp)++	X	X		X		X		X			X		
Urinalysis	X	X		X		X		X			X		
COGNITIVE MEASURES+													
General Intelligence – WISC V		X				X					X		
Inhibition, shifting, verbal fluency – D-KEFS		X				X					X		
Memory: visual recognition, verbal recall - CHAMP		X				X					X		
Memory validity profile - MVP		X				X					X		
Executive functions at home - BRIEF		X				X					X		
MAGNETIC RESONANCE IMAGING (PATHWAYS CONNECT) ##													
Structural/functional Imaging – s/fMRI		X					X				X^^		
ONGOING													
***Adverse events log													X
***Concomitant medications log													X
Withdrawal visit													X
Withdrawal form													X
PHARMACY													

The electronic version of this document is the latest version. It is responsibility of the individual to ensure that any paper material is the current version. Printed material is uncontrolled documentation.

Timepoint/Event	Screening (≤ 12 weeks to Day 0)	Baseline (Day 0)	Month 3 [+/- 2 weeks]	Month 6 [+/- 2 weeks]	Month 9 [+/- 2 weeks]	Month 12 [+/- 4 weeks]	Month 15 [+/- 2 weeks]	Month 18 [+/- 6 weeks]	Month 21 [+/- 2 weeks]	Primary outcome Month 24 [+/- 8 weeks]	Ongoing*
Study medication dispensing/administration		X		X	X+++	X	X+++	X	X+++	X	
Study medication dosing log											X
Legend											
# Not required if already captured as part of PATHWAYS HORIZON ## At baseline and Month 24 only for HORIZON INTENSIVE participants * All ongoing forms to be reviewed and updated at each visit ** Tanner staging optional at Months 12, & 24 for immediate GnRHa participants; Month 24 optional for delayed GnRHa participants ***Safety review including vital signs, adverse event reporting, concomitant medication review, pregnancy test (POCBP only) at every injection visit for participants switching to 3-monthly or monthly IMP preparation.											+ Baseline and 24 months only for HORIZON INTENSIVE participants ++ People of child bearing potential only +++ Dispensing at Months 9,15,21 if changing to 3 monthly preparation ^ Bone age scan at M12 & M24 optional ^^ Visit window for final scan of 6 weeks prior to/following final treatment injection ^^^Gender Identity Questionnaire completed only at baseline for Parents ### Ongoing questionnaires and DEXA scans completed annually during follow up period

Table 2. Schedule of events

The electronic version of this document is the latest version. It is responsibility of the individual to ensure that any paper material is the current version. Printed material is uncontrolled documentation.

4.2 Visit Windows

Note. Please refer to Appendix A for individual Schedule of Events for the immediate and delayed treatment arms in PATHWAYS TRIAL, PATHWAYS HORIZON INTENSIVE, and PATHWAYS CONNECT.

4.2.1 TRIAL

Windows for data collection and drug administration are as follows (as per the Schedule of Events in table 2): month 6 +/- 2 weeks; month 12 +/- 4 weeks; month 18 +/- 6 weeks; month 24 +/- 8 weeks. For visits at month 3,9,15 and 21, visit windows are +/- 2 weeks.

In the event a visit falls outside of the target visit window, the visit should be scheduled as soon as possible and the data entered into the relevant visit. Subsequent visits should follow the original visit schedule. If the visit does not occur within the upper bound of the visit window, the treatment will still be delivered however it will be recorded as a major protocol deviation.

For DEXA and bone age X-Rays, baseline scans must be before the first injection. Thereafter, assessments should be conducted within the window specified for each follow up visit.

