A delayed start comparison provides three time points within the trial: baseline, midpoint, when the immediate start but not the delayed start have received the

The electronic version of this document is the latest version. It is responsibility of the individual to ensure that any paper material is the current version. Printed material is uncontrolled documentation.

intervention, and endpoint, when both have received the intervention but for different lengths of time (see flow chart). Midpoint results provide the comparison of GnRHa vs no endocrine treatment while endpoint results provide insights into the effects of timing of GnRHa and its cumulative effects. For midpoint results, therefore, the length of the delay is critical to ensure the two arms have sufficient time to diverge, for both positive and potential adverse effects, while not being so long that CYP complete pubertal development.

We hypothesise two main effects driving outcomes:

1. Early benefits, which may or may not endure. This will include the expectancy effects of the perceived benefits of GnRHa, mainly affecting symptoms of anxiety, depression and suicidality. We will obtain a baseline measure of the strength of preference for immediate vs delayed intervention and measurement of the above traits (RCADS and ASQ, Schedule of Events) after informing participants of their trial allocation and before GnRHa injection. Participants randomised to a delayed start and expressing a strong preference for immediate intervention may show deterioration from their baseline scores. Expectation effects could be short-lived for the immediate-start group, with scores regressing to baseline. It is also possible that GnRHa leads to a more consistent reduction in distress, which allows CYP to make real gains in other aspects of psychosocial function, including improved self-confidence, peer relations, school engagement and learning (all nominated by CYP as important outcomes). To track this, we will continue to obtain the RCADS and ASQ at 3, 6, 12, (midpoint) 15 and 18 months. These immediate benefits will show the greatest separation between groups at the midpoint assessment.

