4.2.3 CONNECT

For MRI scans, baseline scans must be undertaken prior to the first injection. For delayed-start participants, this also applies to their scan at midpoint, i.e., before their first injection. Otherwise, scans should be within a four week window either side of the midpoint or endpoint date.

Cognitive assessments will ideally take place on the same date as the baseline, midpoint and endpoint injection but otherwise the windows of four weeks either side apply.

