4.9 Data Entry

Randomisation of participants will be undertaken as per the Randomisation instructions provided separately to sites.

Source data will be entered in the EDC by authorised site staff, typically within 7 days of data collection by going to www.ctu.co.uk and clicking the link to Medrio EDCs.

A full audit trail of data entry and any subsequent changes will be automatically date and time stamped, alongside information about the user making the entry/changes.

It is the responsibility of the site PI team to ensure all baseline data are collected before a participant is randomised.

The electronic version of this document is the latest version. It is responsibility of the individual to ensure that any paper material is the current version. Printed material is uncontrolled documentation.

Source data worksheets (SDWs) will be supplied to all recruiting sites by the Trial Manager. These will be prepared after the database specification is finalised and database testing is complete.

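### Assessment-order rules are incomplete at month 12 and contradictory at baseline, so the delayed arm's midpoint measures can follow its first injection

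*Protocol*

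**What the plan says.** **Month 12.** Section 2.2 describes the midpoint as the time when the immediate arm but not the delayed arm has been treated, and as the comparison of GnRHa with no endocrine treatment. Table 5 puts the delayed arm's first dose at month 12. Section 4.2.1 sets one window for both activities ("Windows for data collection and drug administration are as follows"), namely "month 12 +/- 4 weeks; month 18 +/- 6 weeks; month 24 +/- 8 weeks". For DEXA and bone age it adds that "baseline scans must be before the first injection. Thereafter, assessments should be conducted within the window specified for each follow up visit".

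Section 4.2.3 protects the MRI: "For delayed-start participants, this also applies to their scan at midpoint, i.e., before their first injection". Section 4.14.3 does the same for the delayed arm's month-12 clinical Tanner staging. For cognition, section 4.2.3 says that the tests will "ideally take place on the same date as the baseline, midpoint and endpoint injection but otherwise the windows of four weeks either side apply".

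**Baseline.** Section 4.9 makes the site team responsible to "ensure all baseline data are collected before a participant is randomised". Section 4.4 has the first dose given on the day of randomisation. Section 2.2 promises a baseline measure of how strongly participants prefer immediate over delayed treatment, and a symptom measurement ("RCADS and ASQ, Schedule of Events) after informing participants of their trial allocation and before GnRHa injection"). Tables 2, 4 and 5 show one baseline mark each for RCADS and ASQ, and no preference row.

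**The concern.** The midpoint contrast is interpretable as treated versus untreated only if the delayed arm is untreated when measured. The authors recognised this for MRI and Tanner staging. No equivalent statement covers DEXA, cognition or the questionnaires, so a site can follow the protocol and still collect delayed-arm data after treatment has begun. Any early effect of the injection, or of knowing that treatment has started, then appears in both arms and the difference shrinks. Assessment order cannot be restored in the analysis.

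The exposure matters most for outcomes whose first follow-up assessment is month 12: DEXA, the cognitive battery, UGDS-GS and BIS-GS. For these the schedule holds no earlier assessment to fall back on.

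At baseline, sections 13.5.1.1 and 13.5.2.1.1 adjust each continuous outcome for its own baseline score. That score should be one that allocation cannot have influenced. Three sections give different answers about when it is collected.

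**Working it through.** The plan states no figure on this point, so there is none to reproduce. The check is window arithmetic and a comparison of sections.

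**Step 1: possible exposure at month 12.** Take month 12 as week 52. A window of 4 weeks either side runs from week 48 to week 56 and applies to both the injection and the assessment (section 4.2.1).

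- Largest exposure = latest assessment − earliest injection = 56 − 48 = 8 weeks.
- Cognition, with the four weeks counted from the injection as section 4.2.3 is worded: at most 4 weeks. If they are counted from the midpoint date, as in the sentence before it, the bound is again 56 − 48 = 8 weeks.
- If every assessment preceded the injection: 0 weeks.

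**Step 2: share of the contrast kept, if effects build up linearly (assumption).** With assessment at week *t* and delayed-arm exposure *e*, the share is (*t* − *e*)/*t*.

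| Injection week | Assessment week | *e* | Share kept |
|---|---|---|---|
| 48 | 56 | 8 | 48/56 = 0.857 |
| 52 | 56 | 4 | 52/56 = 0.929 |
| 48 | 52 | 4 | 48/52 = 0.923 |
| 52 | 52 | 0 | 1.000 |

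These shares apply if every delayed-arm participant is at the stated extreme. Otherwise, if a fraction *f* is assessed after injection and a fraction *r* of the full effect is already present, the share kept is 1 − *f* × *r*. With *f* = 0.5 and *r* = 8/56 = 0.143 it is 0.93. With *f* = 0.5 and *r* = 0.5, an effect that appears largely at once, it is 0.75. The protocol gives neither *f* nor *r*, so these are illustrations.

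**Step 3: which month-12 outcomes have an order rule?**

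| Outcome | Rule for the delayed arm |
|---|---|
| MRI | before first injection (4.2.3) |
| Clinical Tanner stage | before first injection (4.14.3) |
| DEXA | within the window only (4.2.1) |
| Cognition | either side of the injection (4.2.3) |
| Questionnaires | visit window; responses reviewed before clinic appointments (4.12) |

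**Step 4: baseline sections side by side.**

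- Section 4.9: all baseline data before randomisation.
- Section 4.2.3: names the baseline injection and then allows four weeks either side. Because the immediate arm is dosed on the day of randomisation (4.4), this can be read as allowing baseline cognition up to 4 weeks after treatment starts. Section 4.9 forbids that.
- Section 2.2: an RCADS/ASQ measurement after allocation is disclosed. Under section 4.9 this cannot be the baseline measurement, yet the schedules contain only one at Day 0.
- Section 2.2: a preference measure. The nearest schedule row, personal priorities (4.12.2.4), weights outcome domains, which is a different question.

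**The case against.** The strongest reply is that the damage is limited, and much of it stands.

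- *The primary analysis is safe.* A reader might infer that the trial's main contrast is biased. It is not directly touched: the primary estimand is the 24-month difference (13.5.1.1).
- *Month 12 is not the only untreated comparison.* A reader might infer that it is. But the delayed arm is also untreated at months 3 and 6, when RCADS and ASQ are taken, and at month 6 for KIDSCREEN-10 (Table 2). Those randomised contrasts cover the outcomes for which section 2.2 mainly expects expectancy effects.
- *Baseline is not unprotected.* A reader might infer that RCADS and ASQ covariates are contaminated by allocation or injection, so that adjusted effects are biased. Section 4.9 forbids post-randomisation baseline data, section 2.2 keeps this measurement before the injection, and section 2.2 speaks of deterioration from baseline scores, which implies an earlier, separate baseline. The natural reading is an extra measurement that the schedule omits.
- *The cognition window may not apply to baseline.* It may refer back to the MRI sentence, which defines four weeks around the midpoint or endpoint date. The wording is ambiguous rather than a clear permission.
- *Some order is implied.* The delayed arm's 12-month hormone tests screen for off-trial GnRHa use (3.2.1.5), which makes sense only before dosing, and section 4.12 has responses reviewed before clinic. That protection is partial, since home completion is allowed and staff chase forms up to the end of the timepoint (7.1.1.1).
- *Slow outcomes hardly move in weeks.* Section 2.2 cites bone changes by one year and IQ changes over more than two years.

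None of this supplies an order rule for month-12 DEXA, cognition or questionnaires, or reconciles sections 2.2, 4.2.3 and 4.9.

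**Conclusion.** The point holds in a limited form. At month 12 the order rules are incomplete: compliant scheduling allows up to 8 weeks of delayed-arm exposure, or 4 for cognition counted from the injection. The effect is dilution of the midpoint contrast, of greatest concern for DEXA, cognition, UGDS-GS and BIS-GS. Its size is unknown. If effects build up linearly, about 86% is kept at the 8-week extreme and about 93% at 4 weeks. The loss could be larger for an effect that appears at once, but the documents give neither the speed of onset nor the share of participants assessed after injection. A specific loss in standard deviations, or one scaled to the 0.525 stated for KIDSCREEN-10, is therefore not supported.

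At baseline the fault is contradiction and omission: three sections disagree, and two promised measures are unscheduled. It does not show that the covariates will be biased. This should be fixed before recruitment, but it does not threaten the primary analysis.

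**What to change.** Reconcile sections 2.2, 4.2.1, 4.2.3 and 4.9 with Tables 2, 4 and 5 so that:

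1. all baseline outcomes, including cognition, are completed before randomisation, and the cognition window is stated not to extend past it;
2. all month-12 outcome assessments (questionnaires, cognition, DEXA) are completed before that visit's injection, in both arms so that procedures match;
3. the RCADS/ASQ measurement after allocation and before injection, and the pre-randomisation preference item, each have their own row;
4. only pre-randomisation scores serve as baseline covariates.

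The cost is slightly tighter booking of cognition and DEXA at month 12, one repeat of RCADS and ASQ (5 + 1 = 6 minutes by the durations in section 4.12.2), and a short preference item. No extra visit is needed. The change orders assessments around the injection and alters no dose or treatment rule.
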